**Safety and Feasibility of Single Port Robot in Colorectal Procedures**

**NCT: Unavailable at this time**

**September 24, 2018**

## SP Robot Study

### **1. Purpose:**

The purpose of this study is to evaluate the safety and feasibility of using the SP robot to perform single port robotic colon resection and transanal robotic surgery. The hypothesis of the study is that the SP robot will prove a safe effective modality to perform these procedures.

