### **2. Subject Recruitment and Selection:**

The goal of the study will be to recruit 200 patients between the ages of 18 and 95 years of age, either male or female. Exclusion criteria would include emergency surgery and an inability to offer informed consent. There will be no inducement to the patients, pregnant women would be excluded as well.

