### **4. Background:**

Minimally invasive colorectal surgery was first described in 1991 and has been adopted steadily in the United States in the ensuing 25 years. Offshoots of a laparoscopic approach in a multiport fashion has led to the development of the single port colorectal surgery first described in 2008 performed by, Lankenau trained fellow, [name]. Robotic surgery has been utilized for a full spectrum of abdominal surgery being performed. In the colorectal arena, the robotic approach for benign and malignant

disease is well established, with a great deal of literature generated regarding the safety and benefits of a colorectal robotic approach for benign and malignant disease. The section of colorectal surgery at the Lankenau Medical Center has been an active and robust contributor to surgical literature on laparoscopic surgery, robotic colorectal surgery, and single port laparoscopic surgery. Its one investigator has been involved in the development of clinical applications to the single port robotic platform where this has been utilized in cadaver work that has been published. Recently, the SP robot has gone through FDA clearance and is now available for clinical utilization. The FDA approval is for urologic surgery. The SP robot will be utilized in the same fashion to perform the same colorectal operations that we have been performing with multiple port placements in the past to accomplish robotic surgery in a single port platform in the colorectal arena. The principal investigator has worked on the SP robot over the past 3 years with extensive cadaver experience to develop its safe application in the colorectal field. This study will entail a collection of demographics, preoperative, perioperative and postoperative outcomes of the patients into a database to follow this, report on the outcomes, and notably answer questions to demonstrate the feasibility and safety of this approach in colorectal patients.

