## **5. Research:**

All patients being considered for minimally invasive colorectal surgery will be evaluated for participation in the above study. The original goal will be 200 patients. All of these patients will undergo a standard minimally invasive resection in the same fashion as would be carried out with multiport laparoscopic or robotic surgery. The difference being that the operation would be performed with the single port robot as opposed to multiport robotic or laparoscopic surgery or single port-laparoscopic surgery. The exact same standard of operative care will be employed with these patients. Additional laparoscopic

ports would be utilized as needed to carry out the operation safely at the discretion of the principal investigator. The original target would be for 200 patients, this will then be continued based upon findings, safety and efficacy of this approach, and improved data in the database for further analysis. A preliminary safety analysis will be performed after 10, 20, and 40 patients and shared with the IRB to confirm the safety of this approach. Preoperative demographic information will be collected as well as perioperative outcomes and postoperative outcomes. Any preoperative data will include data related to age, gender, disease state, anatomic location, BMI, ASA classification, previous surgery and previous radiation therapy. The operative data will include time of surgery, total operative time, blood loss, disposable instrumentation utilized, cost data, assistants in the case, robotic console time, complications, IV fluids, blood transfusions, estimated blood loss, urine output, type of anastomosis, how the anastomosis was performed, and conversion rate to multiport surgery. In order to gauge the effect of the surgery on patients' quality of life, the following questionnaires will be administered pre-operatively and post-operatively: SF-36 and QoR-40. Because a validated survey for patient reporting of scarring outcomes does not currently exist, a comprehensive survey (known as the Patient Scar Assessment Questionnaire, PSAQ) whose validity and reliability has been reviewed will be utilized. A photo-series questionnaire, modeled after Dunker et al.'s widely used survey will also be used to help evaluate the cosmetic consequences of scarring and patient's preferences for future surgical approaches (open, laparoscopic, or single port).

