Patients will be monitored for postoperative pain requirements (we will measure the total amount of narcotics used postoperatively per day), postoperative pain score, time to tolerating clear liquids, time to tolerating solid food, time to flatus, time to defecation, time to discharge, readmission rates will be tracked, as well as short term perioperative complications for 30 days or less. All these data will be compared to those from multiport

laparoscopic cases from previously published studies. Post-operative complication rates will be compared using the t-test. Subject data will be stored for the length of the IRB approved study and if we wish to continue using the data another IRB protocol will be submitted for approval. As an ongoing adjunct to this study long term complications including bowel obstruction, hernia rate and anastomotic problems will be noted. These data points will be noted for the length of the study, and we will seek another IRB approval to get longer term outcomes.

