## **6. Risk Assessments to the Patient:**

The risk to the patient would be the same as one with undergoing any major colorectal resection. This would include bleeding, infection, injury to other organs, bladder dysfunction, sexual dysfunction, the need for temporary stoma, permanent stoma and even death. These are inherent to this form of surgery represent the same risks done in an open, multiport laparoscopic, single port laparoscopic, or multiport robotic fashion. However this is the first time an SP robot will be used in humans for colorectal procedures. As such different complications rates may be encountered. Possible benefits to the subject would include decreased pain from less incisions and improved cosmesis with only one incision. Other potential benefits which have been seen in the single port literature have been decreased operative time, reduced blood loss, and a lower hernia rate. It does not seem to be any inherent risk singularly attributable to this robotic approach that would not be ongoing with other standard approaches currently employed. Potential risks would be minimized by the ability to add additional laparoscopic ports in the situation where adequate progress was not being achieved in a robotic single port fashion.

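### The aim is to show that the SP robot is safe, but the one test named for complications looks for a difference and cannot rule out an excess

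*Protocol*

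**What the plan says.** Protocol section 1 gives the hypothesis: "The hypothesis of the study is that the SP robot will prove a safe effective modality to perform these procedures". Section 4 says that the collected outcomes should "notably answer questions to demonstrate the feasibility and safety of this approach in colorectal patients". Section 2 sets the size of this single-arm study: "The goal of the study will be to recruit 200 patients".

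Section 5 tracks "short term perioperative complications for 30 days or less" and takes its comparator from multiport "laparoscopic cases from previously published studies". It then names the method: "Post-operative complication rates will be compared using the t-test". No other inferential method is named for complications. Sidedness, significance level, comparator rate and comparator size are not given.

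Two further passages bear on the point. Section 6 notes that the robot is new to human colorectal surgery and adds: "As such different complications rates may be encountered". Section 5 says of recruitment after the first 200 patients that "this will then be continued based upon findings, safety and efficacy of this approach".

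Section 5 also provides for safety reviews at 10, 20 and 40 patients, to be shared with the IRB.

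**The concern.** Safety is a claim that complications are not materially more frequent than with the established approach. Evidence for it comes from showing that a material excess is incompatible with the data. A t-test of equality asks the opposite question: it looks for evidence that the rates differ. If it finds none, either the rates are similar or 200 patients were too few to tell, and the p-value does not distinguish the two.

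The stakes are practical. The protocol itself expects that complication rates may differ with a platform new to this field, and it lets the safety findings influence whether the series goes on. If the only formal result were a non-significant p-value, a reader could take it as support for safety when the data still allow a substantial excess.

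**Working it through.** There is no figure in the protocol to reproduce: the 200 is a recruitment goal with no rate, significance level, power or margin attached.

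**Inputs.** From the protocol: n = 200 SP patients, a t-test, a published comparator. Assumed here: two-sided 0.05; a published rate p0 of 20%, varied to 10% and 30%; the published rate first treated as a fixed constant, then as an estimate from N = 200 to 2000 cases.

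**Step 1. One example.** Suppose 51 of 200 patients have a complication, so p = 0.255.

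- One-sample t-test: t = (p − p0) / √[p(1 − p)/(n − 1)] = 0.055 / √(0.255 × 0.745 / 199) = 0.055 / 0.0309 = 1.78 on 199 degrees of freedom, two-sided p = 0.077.
- Exact binomial test against 20%: p = 0.063.
- Exact (Clopper-Pearson) 95% confidence interval for the rate: 19.6% to 32.1%.
- Largest excess not excluded: 32.1 − 20 = about 12 percentage points.

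The result is non-significant, yet compatible with no excess and with an excess of about 12 points.

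**Step 2. Allowing for uncertainty in the published rate** (observed 25.5% against 20%, Welch t-test):

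| Published N | p | 95% CI for the difference (points) |
|---|---|---|
| 200 | 0.190 | −2.7 to +13.7 |
| 500 | 0.124 | −1.5 to +12.5 |
| 1000 | 0.101 | −1.1 to +12.1 |
| 2000 | 0.089 | −0.8 to +11.8 |

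**Step 3. How often a true excess would be missed.** For each fixed p0, find the smallest count above p0 that the t-test rejects, then sum the binomial probabilities below it at the true rate.

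| Fixed p0 | Rejects from | Missed, +5 points | Missed, +10 points |
|---|---|---|---|
| 10% | 30/200 | 47% | 3% |
| 20% | 53/200 | 66% | 12% |
| 30% | 74/200 | 70% | 17% |

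With a published rate of 20% estimated from 200 to 2000 cases, the miss rates are 61–78% for a 5-point excess and 11–36% for a 10-point excess, over the Welch and pooled forms of the test. The highest values belong to N = 200.

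**Step 4. Is the example special?** Partly. At a 20% reference, 51 is the last count that the exact test leaves non-significant. At 52/200 the exact test gives p = 0.042 and the t-test p = 0.055. The same pattern appears at other assumed rates: 28/200 against 10% gives t-test p = 0.105 with an exact interval of 9.5% to 19.6%, and 72/200 against 30% gives p = 0.079 with 29.4% to 43.1%.

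**The case against.** A reader might infer that the protocol treats a non-significant t-test as proof of safety, or that the t-test is its safety decision rule. The text supports neither. It is silent on how a non-significant result would be read, and the sentence on continuing past 200 patients does not mention the test. Descriptive complication rates and the reviews at 10, 20 and 40 patients also inform the judgement, and nothing here criticises them.

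Other objections carry weight. The null value and sidedness are not stated, so a test of equality is the ordinary reading and not a quoted fact. The calculation behind a t-test also yields a confidence interval, which the protocol does not forbid. A margin or a rule of interpretation could sit in a statistical analysis plan that is not shown, so its absence is no fault. Every rate above is assumed, the example count lies at the edge of significance, and no passage says that a 5-point excess is the one that matters.

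These points limit the finding without removing it. The protocol chose a method, attached it to the main safety outcome, and chose one that does not answer the question it poses. That sentence needs changing whatever an analysis plan may add.

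**Conclusion.** The point holds as a mismatch between a stated aim and a stated method: showing safety on the one hand, testing for a difference on the other. It does not show that the protocol draws an unsound conclusion, because it states none.

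The size depends on assumptions. With 200 patients and published rates of 10% to 30% taken as fixed, non-significance is weak reassurance about a 5-point excess (missed in 47% to 70% of trials) and fairly good reassurance about a 10-point excess (missed in 3% to 17%). With a small published comparator the latter weakens too: 36% at a 20% rate and N = 200. The logical point, that non-significance alone does not exclude an excess, needs none of these figures. It ranks as a cheap improvement.

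**What to change.** In Protocol section 5, replace the t-test sentence with:

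> The SP 30-day complication rate will be reported with its exact 95% CI, and its difference from the published multiport rate with a 95% CI. The safety conclusion will consider the upper confidence limit, and a non-significant difference will not be taken as evidence of safety.

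A reference rate or maximum acceptable rate stated in advance would sharpen this, but it is optional and for the investigators to choose. Before choosing, they should know what 200 patients can support. At a true rate of 20%, the exact upper limit falls below 25% in 34% of trials, below 28% in 74% and below 30% in 91%. At a true 25% it still falls below 30% in about 35%. A tight limit is therefore hard to meet, and a loose one leaves smaller excesses open.

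The cost is wording only, with no extra patients or data. The safety conclusion may become more modest. A confidence interval also does not remove differences in case mix: the study covers both colon resection and transanal surgery, while the comparator is published multiport laparoscopic cases. The comparison stays indirect with either method.

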## **6. Risk Assessments to the Patient:**

The risk to the patient would be the same as one with undergoing any major colorectal resection. This would include bleeding, infection, injury to other organs, bladder dysfunction, sexual dysfunction, the need for temporary stoma, permanent stoma and even death. These are inherent to this form of surgery represent the same risks done in an open, multiport laparoscopic, single port laparoscopic, or multiport robotic fashion. However this is the first time an SP robot will be used in humans for colorectal procedures. As such different complications rates may be encountered. Possible benefits to the subject would include decreased pain from less incisions and improved cosmesis with only one incision. Other potential benefits which have been seen in the single port literature have been decreased operative time, reduced blood loss, and a lower hernia rate. It does not seem to be any inherent risk singularly attributable to this robotic approach that would not be ongoing with other standard approaches currently employed. Potential risks would be minimized by the ability to add additional laparoscopic ports in the situation where adequate progress was not being achieved in a robotic single port fashion.

## **7. Confidentiality:**

Data will be collected by the research assistant and will be kept in a file protected by a password. All data will be de-identified and upon publication there will not be any reference that could relate to patients identity. Information will be protected under the Health Information Portability and Accountability Act (HIPAA).

